1. BACKGROUND

Epidemiology and clinical significance of Giardia lamblia infections

Giardia lamblia (G.lamblia) is a protozoan which infects small intestine of humans and other mammals. Ingestion of food or water contaminated with cysts represents the common route of transmission. The incubation period lasts from 7 to 28 days. In Nordic countries, including Finland, prevalence of giardiasis is 5.81 % in symptomatic population (Hörmann, 2004). Infected persons can remain asymptomatic or present with a variety of symptoms, ranging from self-limited acute diarrhea to a chronic disease with abdominal pain, diarrhea, and failure to thrive.

Diagnostic tests

Giardiasis is commonly diagnosed by analyzing fecal samples and detecting G.lamblia cysts on microscopy. However, this method requires repeated stool samples to detect intermittent shedding of G.lamblia, e.g. when assessing the response to treatment. Whereas a single positive stool enzyme immunoassay (EIA) for G.lamblia antigen provides a sensitivity close to 100% and specificity of >90% for diagnosis of giardiasis (Jahan, 2014).

Treatment regimens

Nitroimidazoles (metronidazole, tinidazole and others) represent drugs of choice for giardiasis. Tinidazole given orally at a single dose of 50 mg/kg cures 72-100% of the patients (Escobedo, 2007). Trials examining oral metronidazole implicate different regimens of single and multiple daily doses for 1 to 10 days, resulting in variable cure rates. Metronidazole efficacy improves when prolonged (>1 day) treatment courses are administered, compared to single-dose therapy. Rectal tinidazole preparation has been used for years in giardiasis treatment in Finland resulting in a satisfactory response rate, until the drug became unavailable. This treatment option has been particularly useful in children unable to tolerate oral tinidazole due to its unpleasant taste. Rectally administered metronidazole reaches therapeutical concentrations in plasma and has been highly effective in treatment of e.g. vaginal trichomoniasis (Panja, 1982). Rectal administration of metronidazole results in lower serum concentrations, necessitating higher dosage (Lau, 1992). Side effects of nitroimidazoles are usually mild and self-limited. They include abdominal pain, nausea, diarrhea, metallic/bitter taste, headache and dizziness.

2. RATIONALE FOR THE PRESENT STUDY

While oral nitroimidazoles are the drugs of choice for lambliosis, the efficacy and safety of rectally delivered preparations remains unknown. Oral administration of nitroimidazoles in children often proves difficult due to the absence of palatable pediatric formulations. Some children refuse to swallow the medicine or vomit it out. Parents often fail to give oral tinidazole at home, which necessitates controlled drug administration in the hospital, and sometimes even nasogastric tube placement. Thus, a rectally administered drug may represent a solution for the treatment of children who are unable to take oral preparations.

3. AIMS

This study investigates the efficacy and safety of rectally administered metronidazole, as well as the acceptance of this treatment regimen by patients/caregivers. We hypothesize that rectal metronidazole is non-inferior to single-dose of oral tinidazole and will cure at least 72% of patients. We also hypothesize that rectal metronidazole will be tolerated as good as tinidazole. This study will provide significant data on the new option for treatment of giardiasis. The results will be published as a single article in an international journal in the field of pediatrics/parasitology.

4. PATIENTS

We will recruit approximately 180 children (age 6 months to 10 years) whose clinical symptoms could be explained by giardiasis and whose fecal samples will test positive for the presence of *G. lamblia* in Uusimaa laboratory (HUSLAB). Exclusion criteria will be: 1) age <6 mo or >10 years, 2) weight <9.5 kg, 3) the absence of symptoms, 4) co-infection with another pathogen, which may cause giardiasis-like symptoms.

5. METHODS

- 1) The Epidemiologic operations unit of the City of Helsinki will issue information about our study to all its health stations. This note will contain information about the possibility to refer a child with diagnosed *G. lamblia* infection for ambulatory treatment to Children's Hospital, Helsinki University Central Hospital. Researchers will contact the referred patients/caregivers and invite them to participate in the study. If the family refuses the participation, this will not affect the availability and quality of treatment and standard care will be provided to the patient referred.
- 2) In case the primary diagnosis of *G. lamblia* infection is done by finding a positive *G. lamblia* antigen from fecal samples, we will perform additional microscopy examination of stool specimens to exclude other possible parasites/protozoa as a cause of patients symptoms.
- 3) Clinical data on the patient's symptoms will be collected during interviews at the clinical visits and by phone interviews after treatment. A structured questionnaire will assess clinical treatment response, acceptance and possible side effects.
- 4) The study will be performed as an open-label trial. We will randomize patients during primary visits alternately into two groups by random allocation to receive either of the two study drugs.
- 5) Patients from group 1 will be treated with a standard regimen of oral tinidazole (Fasigyn) at a single dose of 50 mg/kg, maximum 2 g/dose. Patients from group 2 will be given rectal metronidazole (Flagyl) 500 mg/dose for children weighing 10–14,9 kg, 1000 mg/dose for those weighing 15–29,9 kg and 1500 mg/dose for those weighing 30–44,9 kg. Suppositories will not be halved. Patients will be given 1 dose/day for 3 days. The first dose of metronidazole will be administered during the primary clinical visit and 2 additional doses will be provided to the parents for home administration.
- 6) Fecal samples will be collected from the study patients on day 7-10 post-treatment and will be analyzed in HUSLAB for the presence of *G. lamblia* antigen by EIA. Early collection of samples on day 7-10 will help to avoid the risk of tests being positive due to reinfection.

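### The allocation sentence prescribes both alternation and random allocation; followed literally, alternation would make 179 of 180 assignments known in advance

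*Protocol*

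**What the plan says.** Section 5 (Methods), item 4 is the only statement on how children are assigned: "We will randomize patients during primary visits alternately into two groups by random allocation to receive either of the two study drugs". The sentence before it reads "The study will be performed as an open-label trial".

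Four other statements bear on the point:

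- **Recruitment (Section 5, item 1).** Children are referred "for ambulatory treatment to Children's Hospital, Helsinki University Central Hospital". Then: "Researchers will contact the referred patients/caregivers and invite them to participate in the study".
- **Treatment (Section 5, item 5).** One arm receives an oral drug and the other a rectal drug. For the rectal arm: "The first dose of metronidazole will be administered during the primary clinical visit".
- **Size (Section 4).** About 180 children are planned.
- **Hypothesis (Section 3).** "We hypothesize that rectal metronidazole is non-inferior to single-dose of oral tinidazole and will cure at least 72% of patients".

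**The concern.** The sentence gives two instructions that cannot both be carried out. Assigning children "alternately into two groups" means that each child gets the opposite of the previous child's arm. Random allocation means that the previous arm does not determine the next one. A member of staff working from the protocol could reasonably do either.

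The surrounding design makes the literal reading matter. The drug given is visible to everyone. Only one treating hospital is named, so nothing suggests several parallel sequences. The researchers who run the trial also invite the families, and allocation follows at the primary visit. On the literal reading they can know the next arm before they decide whom to invite or when to see a child.

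Section 2 also supplies a plausible motive. It reports that some children refuse or vomit oral medicine and that parents often cannot give it at home. Someone who expects a particular child to struggle with the oral drug, and who knows the next arm, could delay or reorder that child's visit. This shows that steering is possible, not that it will happen.

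Non-inferiority depends on comparable arms. Selection at entry could make the arms differ in prognosis in either direction, and analysis cannot reliably undo that. A trial run by alternation also could not properly be reported as randomised.

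**Working it through.** The protocol gives no figure for the predictability of allocation, so there is none to reproduce. It also gives no non-inferiority margin, rate of steering or prognostic difference, so no bias, power or error rate can be derived. Only foreseeability can be counted.

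**Inputs**

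- N = 180 (Section 4, an approximate number).
- Two arms (Section 5, items 4 and 5).
- Past assignments visible (open-label, oral against rectal).
- Assumption: one allocation list, with the previous assignment known to staff. The single named hospital supports this, but the protocol does not state it.
- Assumption: a 1:1 ratio for the random schemes. Literal alternation implies it; the protocol gives no number.
- Assumption: the block sizes below are illustrations. The protocol mentions no blocks.

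**Strict alternation.** Once the first arm is known, the other N − 1 follow: (180 − 1)/180 = 99.4%. Because N is approximate: 169/170 = 99.4% and 189/190 = 99.5%. If the first arm is also fixed, all 180 are known. If it is random, expected correct guesses are 179 + 0.5 = 179.5.

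**Simple 1:1 randomisation.** No assignment is certain. Expected correct guesses are 180 × 0.5 = 90.

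**Permuted blocks of size 2m.** For an observer who always guesses the under-filled arm, expected correct guesses per block are m + (2^(2m)/C(2m,m) − 1)/2.

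- Size 4: 2 + (16/6 − 1)/2 = 2.833 of 4, or 70.8%.
- Size 6: 3 + (64/20 − 1)/2 = 4.1 of 6, or 68.3%.
- Size 8: 4 + (256/70 − 1)/2 = 5.329 of 8, or 66.6%.
- Sizes 4, 6 and 8 equally likely: (2.833 + 4.1 + 5.329)/18 = 12.262/18, or 68.1%.

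For fixed blocks of 4 of known size, the last place is always certain. The third is certain when the first two match, with probability 1/3. That gives 1.333 per block, and 45 × 1.333 = 60 certain assignments.

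| Scheme | Certain in advance, of 180 | Expected correct guesses, of 180 |
|---|---|---|
| Alternation, random first arm | 179 | 179.5 |
| Simple 1:1 | 0 | 90 |
| Fixed blocks of 4, size known | 60 | 127.5 |
| Fixed blocks of 6 | not computed | 123.0 |
| Blocks varying over 4, 6, 8 | not computed | 122.6 |

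Simulation agrees. With 4,000 sequences the mean correct guesses were 179.5 (alternation), 90.0 (simple), 127.4 (blocks of 4) and 123.0 (blocks of 6). With 20,000 sequences the varying blocks gave 122.4.

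**Hybrid readings.** A random first child followed by alternation is exactly the 179-of-180 case. Randomising the first child of each pair would leave 90 assignments certain and about 135 guessed correctly (1 + (4/2 − 1)/2 = 1.5 of 2, or 75%), but the sentence does not describe that.

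**The case against.** The strongest reply is that the sentence names chance twice and alternation once, so the adverb is probably a slip for *alternatively* or for assignment to one group or the other. On that reading allocation is not predictable and only the wording needs correction. This is fair, and it makes every foreseeability figure here conditional. It does not remove the need to act, because the text cannot settle which was meant and the plain word can be followed as written.

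Second, a family is invited before it is allocated. If several families are pending or some decline, the arm that a given invited child will receive is not yet fixed. This stands in part. The next arm on the list is known at invitation, but which child takes it is firm only at the primary visit, or when no other family is waiting. Steering through the visit or the order of visits remains open.

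Third, the count needs one shared list. With k separate alternating lists, 180 − k assignments are certain, which changes little for small k.

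Fourth, microbiological cure is a laboratory test. That limits biased assessment but gives no protection against selection at entry. Clinical cure in any case rests on reported symptoms.

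Finally, block sizes and the mechanics of concealment may be left to other documents, and their absence is not the complaint. The complaint is that the protocol states two incompatible methods. A later analysis plan cannot change how children have already been assigned.

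**Conclusion.** The concern holds. The only allocation rule in the protocol text available contradicts itself, and nothing there says which term governs. If alternation is followed on one list of 180, 179 assignments (99.4%) are known in advance. The comparable count is none under concealed simple randomisation, and 60 under fixed blocks of 4 of known size.

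Confidence is high for the contradiction and for this conditional count. It does not extend to whether alternation is actually planned, or to any bias, whose size and direction the protocol does not allow one to compute. The point must be resolved before the first child is assigned: the consequence on the literal reading is serious, and the method cannot be changed later for children already allocated.

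**What to change.** In Section 5, item 4, delete the adverb. State that allocation follows a computer-generated random sequence, concealed from those who recruit until eligibility and consent are recorded. If alternation is truly the intended method, delete both references to randomisation instead and describe the trial as quasi-randomised.

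The cost is a one-sentence amendment and the preparation of a concealed list, with no added children or visits. Each random scheme has a modest drawback, and the sponsor can choose between them:

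- **Simple randomisation** allows unequal arms. The 2.5% and 97.5% points of a binomial(180, 0.5) are 77 and 103. A split of 77 against 103 raises the variance of the difference by a factor of (1/77 + 1/103)/(2/90) = 1.021, about 2%.
- **Blocks** keep the arms balanced but leave some predictability, because past arms are visible: about 128 of 180 guessed correctly with fixed blocks of 4, and about 123 with sizes varying over 4, 6 and 8. Alternation gives 179.5 on the same measure.

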6. ETHICAL ASPECTS

The study will provide valuable information on the treatment of giardiasis. All of the study patients will be given treatment for *G. lamblia* infection and to those patients who will not respond to the regimen under evaluation a standard course of therapy will be given.

We will apply for the permissions to carry out the study from the Ethic's Board and Finnish Medicines Agency.

Informed consent will be obtained from the patients/caregivers, as well as from children aged ≥ 7 years.

Clinical and laboratory data will be collected into an electronic database. All the participants will be given codes and personal data will not be recorded. Only researchers listed on page 1 of this protocol will have access to the database.

8. FUNDING

The primary diagnostic tests and follow-up fecal samples belong to the established clinical routine and are a part of standard management of patients with giardiasis. Drugs for the study will be covered by the Hospital for Children and Adolescents, Helsinki University Hospital as a part of routine patients care.

